Clinical Investigation Plan

CP346

PIP 1.0 - Pressure Injury Prevention

Post-market Clinical Follow up study, Biatain Silicone Sacral

August 2022 – December 2022

Title:

A Prospective Single-arm Study Investigating the Safety of Biatain Silicone Sacral While Used as Prevention in Hospital-admitted Patients at Risk of Developing a Pressure Injury

NCT05619003

Document date: 28-03-2023

This confidential document is the property of Coloplast A/S.
No unpublished information contained herein may be
disclosed without written approval of Coloplast A/S.

SYNOPSIS OF THE CLINICAL INVESTIGATION

Title:

A prospective single-arm study investigating the safety of Biatain Silicone Sacral while used as prophylactic prevention amongst hospital admitted patients at risk of developing a pressure injury.

Test products:

Biatain Silicone Sacral is a CE-marked five-layer foam dressing, that has been sold in the US since April 2018. It comes in two sacral sizes, a small heart-shape and a larger diamond-shape.

(The test product is Biatain® Silicone sacral 15 cm x 19 cm / 6 in x 5.5 in. There is no comparator product in this investigation)

Intended use:

The Biatain Silicone Sacral products are sterile packed, single use polyurethane foam dressings with silicone adhesive intended for wound management and can be used as part of a prophylactic therapy to help prevent skin damage e.g., pressure injuries.

Aim and Objectives:

The aim of the clinical investigation is to evaluate safety of Biatain Silicone, when used as prophylactic prevention on hospital-admitted patients at risk of developing a pressure injury.

- **Primary objective:** Evaluate safety

- **Explorative objective:** Establish the proportion of subjects, that develop pressure injuries during hospitalization while wearing Biatain Silicone Sacral bandage

The proportion of hospital-acquired pressure injuries will be compared to relevant existing proportions in literature³.

Design of the investigation:

During the study period, data will be collected to determine a *proportion of hospital acquired pressure injuries in hospital admitted patients with a limited level of mobility*. The study is designed as a non-comparative, single-arm, prospective multi-center observational study. The study will be conducted in Danish hospitals and the establish proportion of hospital-acquired pressure injuries will be compared to global, European, and Scandinavian proportions of hospital-acquired pressure injuries reported in literature.

(The investigation is a non-comparative, single-arm investigation with one test period. In total 67 hospital-admitted patients will be included. Each subject will have daily test-visits overseen by the Principal Investigator

or designee during an expected 7-day test period in total or until the subject is discharged. The subjects will test the CE marked test product Biatain Silicone Sacral 15 cm x 19 cm / 6 in x 5.5 in).

Expected duration of the clinical investigation:

The investigation will be conducted from August 2022 through December 2022.

Primary endpoint:

Number of Adverse Events

Secondary endpoint:

Number of Device Deficiencies

Exploratory endpoint:

Hospital-acquired sacral pressure injuries during investigation period (Yes/No)

Population/subjects:

The subjects to be included in the study will be a range of partially immobilized hospital-admitted patients (from e.g., medical, surgical, lung and orthopedic surgical units) with a Braden score of 6-18.

(Hospital-admitted patients with a limited level of mobility and a Braden score between 6-18).

Inclusion and Exclusion Criteria:

Inclusion criteria	Exclusion criteria
Hospital-admitted patients at risk of developing a pressure injury with an expected hospital-stay of more than 24 hours from time of screening	Suspected or actual spinal injury precluding the patient from being turned
≥18 years of age and has full legal capacity	Sacral erythema, sacral pressure marks, pre-existing sacral pressure injury
Has given written consent to participate by signing the Informed Consent signature Form	Trauma to sacrum.
Has a Braden score of 6-18 at screening (within the last 24 hours or at time of screening) (Appendix 2)	Topical treatment with steroid cream in the sacral area. (treatment must have been terminated at least 14 days prior to enrollment)
Intact sacral skin (non-breached skin, without signs of non-blanchable erythema over bony prominence/pre-existing sacral pressure injury over bony prominence) (Appendix 3)	Pregnancy or breastfeeding

LIST OF ABBREVIATIONS

ABBREVIATION	WRITTEN OUT	EXPLANATION
ADE	Adverse Device Effect	See section 18.2
AE	Adverse Event	See section 18.1
ASADE	Anticipated Serious Adverse Device Effect	See section 18.4.2
CIP	Clinical Investigation Plan	
CIR	Clinical Investigation Report	See section 20
CRF	Case Report Form (paper or electronic)	
CM	Clinical Manager	
DQF	Data Query Forms	A DQF is a query specifically used in clinical research. The DQF is the primary data query tool from the sponsor to clarify discrepancies and ask the investigator for clarification. The DQF is part of the data validation process in a clinical investigation.
DD	Device deficiency	See section 18.3
EC	Ethics Committee	
IB	Investigator's Brochure	Compilation of the current clinical and non-clinical information on the investigational medical device(s,) relevant to the clinical investigation.
IFU	Instruction for Use	Appendix 1
ITT	Intention to Treat	See section 10.1
PI	Principal Investigator	Qualified person responsible for conducting the clinical investigation at an investigation site. If the clinical investigation is conducted by a team of individuals at an investigation site, the PI is the responsible leader of the team. Whether this is the responsibility of an individual or an institution can depend on national regulations.
SADE	Serious Adverse Device Effect	See section 18.4.1
SAE	Serious Adverse Event	See section 18.4
USADE	Unanticipated Serious Adverse Device Effect	See section 18.4.3

> TABLE OF CONTENTS

1. List of personnel involved in the Investigation.....	8
1.1. Sponsor representatives	8
1.2. Investigators.....	8
2. Rational/justification for conducting the clinical investigation	9
3. Objective(s) and hypotheses of the clinical investigation	9
3.1. Aim and Objective	9
4. Investigational device and comparator(s)	9
4.1.1. Manufacturing	10
4.2. Identification and traceability of the device	11
4.3. Intended use of the device in the clinical investigation	11
4.4. Handling of the investigational device	11
4.5. Handling of the investigational device	11
5. Design of the clinical investigation	12
5.1. General	12
5.2. Primary endpoint.....	12
5.3. Secondary Endpoint	12
5.4. Exploratory endpoint	12
5.5. Rationale for selection and measurement of endpoints	13

1.1. Sponsor representatives

1.2. Investigators

2. Rational/justification for conducting the clinical investigation

The Biatain Silicone Sacral and Multishape dressings are multi-layer polyurethane foam dressings. They are CE-marked products and have been on the US market since April 2018. They are evaluated as safe to use and perform according to their intended purpose and indications.

This investigation is a Post-market Clinical Follow-up Study, which aims to support the clinical performance of Biatain Silicone Sacral regarding the use of the dressing as part of prophylactic therapy to help prevent skin damage, e.g. pressure injuries. A pressure injury (PI) or pressure ulcer (PU) is defined as localized damage to the skin and/or underlying tissue, as a result of pressure or pressure in combination with shear. PIs usually occur over a bony prominence but may also be related to a medical device or other object.¹⁻²

The need for follow-up clinical data regarding this indication has been suggested in the Clinical Evaluation for Biatain Silicone Sacral and Multishape, and an outline of investigation CP346 is described in the Post-market Clinical Follow-up section of the Clinical Evaluation Report (CER) VV-0247441 for Biatain Silicone Sacral and Multishape.

3. Objective(s) and hypotheses of the clinical investigation

3.1. Aim and Objective

The aim of the clinical investigation is to evaluate safety of Biatain Silicone, when used as prophylactic prevention on hospital-admitted patients at risk of developing a pressure injury.

- **Primary objective:** Evaluate safety

- **Exploratory objective:** Establish the proportion of subjects, that develop pressure injuries during hospitalization while wearing Biatain Silicone Sacral

[figure not shown]
The proportion of hospital-acquired pressure injuries will be compared to relevant existing proportions in literature³.

4. Investigational device and comparator(s)

The Biatain Silicone Sacral product is a sterile pouch-packed, single use polyurethane foam dressings with silicone adhesive intended for wound management and can be used as part of a prophylactic therapy to help prevent skin damage e.g., pressure injuries.

The Biatain Silicone Sacral and dressings are available in different shapes to fit the sacral area of the body. In this investigation it will primarily be the heart-shaped product, which will be used. However, if needed the diamond shaped, can be chosen.

**Biatain Silicone Sacral,
item no. 39001**

**Biatain Silicone Sacral,
item no. 39000**

Figure 1: Biatain Silicone Sacral dressings.

The two Biatain Silicone Sacral dressings consist of the same five layers:

- Polyurethane (PU) top film – a permeable barrier film of PU that is printed with dots
- Tissue layer – a tissue layer of cellulose fibres
- Super absorber layer – a cellulose fibre matrix with super absorbing particles
- Biatain foam pad – a PU foam with a thickness of 2.3 mm
- Silicone adhesive bi-layer – a silicone adhesive gel

4.1.1. Manufacturing

Biatain Silicone Sacral dressings are single packed in pouches consisting of a top layer of paper and a bottom layer of film. The two layers of primary packaging material (paper/film) are heat welded together, thus creating the pouch, which is the sterile barrier of the product. The Biatain Silicone Sacral products are ethylene oxide sterilised.

The products are packed in a retail box, and the instruction for use (IFU) is a leaflet in the retail box.

4.2. Identification and traceability of the device

Coloplast A/S, [name], is the manufacturer of the CE marked Investigational device (Biatain Silicone).

Item No. 5 digit	Product Name	Actual size: - Total dressing - Absorbing pad	Product Description
39001	Biatain Silicone Sacral	15.0 cm x 19.0 cm	Sacral dressing with dimensions, 15 cm x 19 cm / 6 in x 7.5 in
		10.9 cm x 14.0 cm	Absorbing pad with dimensions, 11 cm x 14 cm / 4.3 in x 5.5 in
39000	Biatain Silicone Sacral	25.0 cm x 25.0 cm	Sacral dressing with dimensions, 25 cm x 25 cm / 9.8 in x 9.8 in
		17.0 cm x 17.2 cm	Absorbing pad with dimensions, 17 cm x 17 cm / 6.7 in x 6.7 in

Table 1: An overview of the item numbers and product variants for Biatain Silicone Sacral.

4.3. Intended use of the device in the clinical investigation

The Biatain Silicone Sacral product is a sterile pouch-packed, single use polyurethane foam dressing with silicone adhesive intended for wound management and can be used as part of a prophylactic therapy to help prevent skin damage e.g., pressure injuries amongst a population with Braden Score 6-18.

4.4. Handling of the investigational device

The handling of Biatain Silicone is described in detail in the Instruction for Use (IFU), which is included in the box following the device. Storage conditions are also stated in the IFU.

The PI (Principal Investigator) and PI delegate will receive training by sponsor and/PI in handling and correct use of the investigational device. The PI or delegate will inform the subjects in the investigational properties of the device.

(Biatain Silicone Sacral, Instruction for Use – Appendix 1)

4.5. Handling of the investigational device

The subjects will be included for up to 7 days.

Subjects that are included in the investigation and applied the investigational product, are expected to wear the product up to 7 days or until discharged. The same product will be applied for the entire test period, however if necessary, due to contamination or rolling edges, the product must be replaced with a new product.

Therefore, the subjects are expected to use approximately 1 product, however the site will be supplied with enough products in case of replacements of products for the duration of the investigation.

In total 67 subjects will be enrolled. To allow for unpredicted dressing changes, 1 patient requires 7 heart shaped/small products, which is per 67 patients: $67 \times 7 = 469$ small sacral products.

Around 30 patients may need the large sacral bandage: $30 \times 7 = 210$ large sacral products.

5. Design of the clinical investigation

5.1. General

The Clinical investigation is an open-labelled, non-comparative, single-arm, prospective, multi-center observational investigation.

Subjects will be applied Biatain Silicone Sacral dressing in the sacral area at Baseline Visit / V1 in a test period up to 7 days or until discharged.

In total, 67 hospital-admitted patients will be enrolled. Each subject will have a screening visit (V0/Day 0), a Baseline visit (V1/Day1) and daily visits (V2/Day2 to V8/termination visit) performed. If the subject is discharged prior to visit 8, the termination visit will be performed at the day of the discharge.

All visits will be carried out by the Principal Investigator or delegate.

Before scheduling V0 the subject will be informed about the investigation, where the PI or delegate will give a detailed information about the requirements, the content and what it involves participating in the investigation. See section 6.4 for recruitment.

Screening visit (V0/Day0) and Baseline visit (V1/Day1) can be performed the same day. If the subject wishes to re-consider his or her participation after Screening (Visit0/Day0), the subject has the right to wait minimum 24 hours before decision to participate. If the subject hereafter decides to participate in the clinical investigation, Baseline visit (V1/Day1) will be scheduled, and the inclusion procedures will be performed. Screening visit/V0 and baseline visit must be performed on following days unless performed the same day.

[figure not shown]

Figure 2: Study Design CP346

5.2. Primary endpoint

Number of Adverse Events

5.3. Secondary Endpoint

Number of Device Deficiencies

5.4. Exploratory endpoint

Hospital-acquired sacral pressure injuries during investigation period (Yes/No)

5.5. Rationale for selection and measurement of endpoints

The primary endpoint, number of adverse events and the secondary endpoint number of device deficiencies, has been chosen to examine the safety of Biatain Silicone Sacral.

The exploratory endpoint, hospital-acquired sacral pressure injuries during investigation period, has been chosen to examine the performance of Biatain Silicone Sacral, regarding its ability to help prevent pressure injuries.

5.6. Demography and potential compromising factors

The subjects should not be treated with topical steroid creams, skin lotions, barrier sprays or barrier wipes in the sacral area during the investigation.

- Gender/age/height/weight.
- Braden Scale Score
- Urine incontinence (y/n)
- Faecal incontinence (y/n)
- Date and primary reason for admission (e.g., diabetes mellitus, cardiovascular disease, renal disease, pulmonary disease, anemia, trauma, other)

5.7. Equipment/methods and timing for assessing the variables

Please go to Flowchart table 5 section 7.2 for information regarding timing of endpoint date capture and section 11 for information about data collection.

5.8. Randomisation Procedure

Subjects are not randomized as the control group comes from the Border Trial Study (3).

5.9. Total expected duration of clinical investigation

The dates below are approximate, and no subjects will be enrolled before all required approvals have been obtained. If changes are required, applicable EC and regulatory authorities will be notified.

First subject enrolled: August 15th 2022.

Last subject enrolled: December 1st 2022.

Last subject completed: December 8th 2022.

Final report: June 2023.

6. Clinical Investigation population

The clinical investigation will be conducted with 67 hospitalized subjects enrolled at 3 clinical investigation sites. Each site will enrol about 22-24 subjects at a competitive rate, until the investigation target of 67 subjects is reached.

According to the sample size calculations (see section 10.2) 50 subjects are required to complete the investigation with at least 24 hours of wear time to be counted as completers. Considering a drop-out rate of 30%, the required total number of subjects to be enrolled in the trial shall be 67.

6.1. Eligibility criteria

To be included in the investigation, the subjects must comply with the selection criteria described below.

6.2. Inclusion criteria and Exclusion criteria

Inclusion criteria	Justification for inclusion criteria
Hospital-admitted patients at risk of developing a pressure injury with an expected hospital-stay of more than 24 hours from visit 1	Intended patient population
≥18 years of age and has full legal capacity	To meet the Helsinki declaration
Has given written consent to participate by signing the Informed Consent signature Form	To meet the Helsinki declaration
Has a Braden score of 6-18 at screening (performed within the last 24 hours) (Appendix 2)	To meet primary endpoint
Intact sacral skin (non-breached skin, without signs of non-blanchable erythema over bony prominence/pre-existing sacral pressure injury over bony prominence) (Appendix 3)	Skin must be intact on admission to detect developing pressure injuries during investigation period

Table 2. Inclusion criteria

Exclusion criteria	Justification for exclusion criteria
Suspected or actual spinal injury precluding the patient from being turned	Turning of the patient (to mobilize them) at regular intervals are a part of standard procedure for pressure injury prevention
Sacral erythema, sacral pressure marks, pre-existing sacral pressure injury	Skin must be intact on admission to detect developing pressure injuries during investigation period
Trauma to sacrum	Skin must be intact on admission to detect developing pressure injuries during investigation period.
Topical treatment with steroid creme in the sacral area (treatment must have been terminated at least 14 days prior to enrollment)	Steroid creme may interfere with the skin condition and make it more fragile
Pregnancy or breastfeeding	Even though the ingredients and recipes have been approved for human beings, their effect on embryos, fetuses and infants are unknown

Table 3. Exclusion criteria

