6.4. Recruitment and enrolment

Recruitment of potential subjects will begin once approval have been obtained from the Ethics Committee (EC).

Recruitment will occur through competitive enrolment at 3 different sites in Denmark. The recruitment period from first subject enrolled to last subject enrolled will be approximately 4 months.

Recruitment from hospitals will be via patient screening visits or subject records kept at the participating sites. The Coloplast Clinical Manager will have close contact to each site during the recruitment and enrolment period.

Sites will be instructed to enrol 22-24 eligible hospitalized subjects at a competitive rate. Once the Coloplast Clinical Manager is aware, that 67 subjects have been enrolled, the recruitment will stop.

If, at this time, there are subjects, who have been informed about the investigation (V0) and are reflecting on participation, they will be given the opportunity to be included within the 24 hours post V0.

Recruitment method	Hospital
Potential subjects	Recruitment will go through the Hospital sites. Potential subjects are identified by screening in patient journals using the following searching criteria: 
 • ≥ 18 years of age • Hospital-admitted patients with a limited level of mobility and a Braden score between 6-18 • Expected hospital stay of at least 72 hours
First contact	The potential subjects will be contacted during a planned visit in the ward at the hospital. If a subject is eligible and interested in participating in the investigation upon a short introduction, then written information about the investigation (Informed Consent Form) will be distributed to the subject. The Principal Investigator or delegate will invite the subject to a Screening Visit (V0).
Screening Visit (V0)	At the scheduled Screening Visit (V0) the Principal Investigator or delegate will introduce the investigation and review the inclusion and exclusion criteria. If the subject wishes to reconsider his/her participation at V0, the subject has the right to wait minimum 24 hours before deciding on participation. If the subject hereafter decides to participate in the clinical investigation a Baseline Visit (V1) will be scheduled unless performed the same day as the Screening Visit. If the subject does not meet the inclusion criteria or meet the exclusion criteria, this will be registered at the Subject Pre-Screening Log.

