6.6. Point of enrolment

A subject is considered enrolled in the investigation when the written Informed Consent is obtained. The expected duration for each subject is described in 5.1.

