7.1. Clinical investigation-related procedures

Screening Visit (V0), Day 0:

- Introduction to the investigation and review of Subject information Form
- Check of in- and exclusion criteria
- Informed Consent Form – ICF signed at Visit 0. If subject wishes to have time for consideration, it is possible and the ICF is signed at Visit 1 the following day
- Inclusion in investigation and allocation of subject number after ICF is signed

Baseline Visit (V1), Day 1:

- Introduction to the investigation and review of Subject information Form
- ICF signed (if not signed at Visit 0)
- Confirmation of inclusion and exclusion criteria if more than 24 hours has passed since Visit 0
- Collect baseline information:
 - Gender (male/female)
 - Age (at time of enrollment (years)
 - Height (cm)
 - Weight (kg)
 - Urinary incontinence (Y/N)
 - Faecal incontinence (Y/N)
 - Date and main reason for admission (e.g., diabetes mellitus, cardiovascular disease, renal disease, pulmonary disease, anaemia, trauma, other)
 - Skin inspection
 - Braden Scale Score
- Apply Biatain Silicone Bandage on the sacral area

Baseline 2-7, skin inspection, Day 2-7:

- Partial lift of test product and skin inspection for signs of non-blanchable erythema over bony prominence/sacral pressure injury over bony prominence

- Re-application of the test product
- Has there been a test product change (Y/N)?
 - if yes, please register what the cause of the change was (dressing soilage, weakened border, damp/saturated dressing, bulky foam, other)

Termination Visit 8, Day 8 or at the day of discharge/earlier termination date:

- Have signs of non-blanchable erythema over bony prominence/sacral pressure injury over bony prominence developed (Y/N)?
 - If yes, please specify stage of pressure injury (*Appendix 3*)
- Was there any non-compliance to the local pressure injury prevention guideline (Y/N)?
 - If yes, explain non-compliance
 - if yes, please include a summary in the comment page

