10.1. Statistical design, method and analytical procedures

Definition of analysis populations

Safety populations and Intention to Treat (ITT) will be defined at a formal data review meeting before database lock. As a minimum, the data manager, the clinical manager and the statistician will be involved in the classification of subjects.

The safety population will be constituted by all subjects with valid informed consent. The ITT population (full analysis set) will be constituted by all subjects with valid informed consent, who have been exposed to the Test Product, with information on at least one endpoint.

The summary of the primary and secondary endpoints will be based upon the safety population, whereas the statistical analysis of the exploratory endpoint will be based on the ITT population. Invalid individual data points may be omitted from analysis even though the corresponding subject is part of the ITT population. Any exclusion of data points will be documented.

A formal per protocol (PP) population is not planned due to the explorative nature of the investigation. Considering the data obtained it might be considered to make additional explorative analyses based on a subset of the ITT population.

Analysis of the endpoints and baseline data.

The endpoints as well as baseline assessments will be listed and summarized by descriptive statistics. The summaries will be made for relevant visits (baseline or V1-V8), separately.

Summary statistics for continuous variables are presented with N, Mean, SD (standard deviation), Median, Min and Max, where N denotes the number of subjects contributing with non-missing data. For discrete variables, summary statistics are presented with N and percentage, where percentage is based on the total number of subjects/observations with non-missing data.

The incidence rate (proportion) of hospital-acquired pressure injuries in hospital-admitted patients will be estimated based on the exploratory endpoint (pressure injuries: Yes/No). The proportion of completed subjects answering "Yes" will be calculated. By use of an exact test in the Binomial distribution a 95% confidence interval will be estimated for the proportion.

All statistical analysis will be performed with SAS (version 9.4/Enterprise Guide version 7.1).

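### The exploratory rate counts sacral injuries from dressing application in patients still injury-free at V0/V1; it is not a hospital-acquired incidence from admission, and comparability with the cited rates is not established

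*Combined protocol and SAP*

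**What the plan says.** The endpoint in section 5.4 is "Hospital-acquired sacral pressure injuries during investigation period (Yes/No"), so only events inside the investigation period count. That period starts late relative to admission. Section 6.6 states: "A subject is considered enrolled in the investigation when the written Informed Consent is obtained". The dressing goes on at V1 (sections 5.1 and 7.1). Section 4.5 adds: "The subjects will be included for up to 7 days", and discharge ends follow-up sooner.

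Recruitment is among people already on the ward. In section 6.4, "Potential subjects are identified by screening in patient journals", followed by an approach on the ward and an invitation to V0. The stay criterion in section 6.2 looks forward only: "with an expected hospital-stay of more than 24 hours from visit 1". The synopsis counts the same 24 hours from screening, and section 6.4 uses a 72-hour expected stay as a search criterion. None of these sets a maximum time since admission.

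Section 6.2 excludes any sacral erythema, pressure mark or existing sacral injury, whatever its origin. The stated reason is "Skin must be intact on admission to detect developing pressure injuries during investigation period". Section 7.1 places the check at V0, with confirmation at V1 if more than 24 hours have passed.

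The analysis in section 10.1 reads: "The incidence rate (proportion) of hospital-acquired pressure injuries in hospital-admitted patients will be estimated based on the exploratory endpoint". Section 10.2 expects to draw comparative conclusions against the control group of a cited randomised trial, 5.3% [2.3%; 10.1%], and against literature rates. Section 10.4 requires the result to be comparable with that control-group figure. Among the baseline items in section 7.1 is "Date and main reason for admission".

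**The concern.** The label and the quantity differ. A patient who develops a sacral injury on hospital day 2 and is screened on day 3 has a hospital-acquired injury, yet is ineligible and contributes nothing. A patient with a week of injury-free stay is eligible and starts at time zero. The sample is therefore conditioned on reaching V0/V1 without injury or erythema, after a delay that may differ between patients and sites.

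A reader of the report would take a hospital-acquired incidence in hospital-admitted patients to cover the stay from admission. The endpoint is exploratory, but it carries the only comparability requirement in the plan (section 10.4). If the external rates were counted on a different basis, a difference from them, or agreement with them, could reflect when counting began and not the dressing.

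**Working it through.** **1. The plan's comparator.** The interval 5.3% [2.3%; 10.1%] matches an exact binomial interval for 8 events in 152 patients (8/152 = 5.3%). The plan does not give these counts. The figure is internally consistent, but it carries no information on when observation began or whether existing injuries were excluded.

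**2. The passages side by side.**

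| Element | What the label implies | What the plan does |
|---|---|---|
| Start of counting | Admission | Dressing application at V1 (5.1, 7.1), after consent (6.6) |
| Injury in hospital before screening | Counted | Patient excluded (6.2) |
| Skin intact at | Admission (6.2 justification) | V0/V1 (7.1) |
| Time since admission | Zero by definition | No limit (6.2, 6.4); no planned analysis by it (10.1) |
| End of counting | Discharge | Day 8 visit or discharge, if earlier (5.1) |

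**3. What follows without further assumptions about risk over time.** Let S(t) be the proportion of an admitted population still free of sacral injury t days after admission. For entry at day d with 7 days of follow-up:

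- from admission to day d+7: 1 − S(d+7)
- measured from entry: 1 − S(d+7)/S(d)
- difference: S(d+7) × (1/S(d) − 1), which is zero or more, and positive if any injury occurs before day d.

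So the measured rate is below the rate from admission to the same day in the same admitted population, meaning with the patients injured before entry put back.

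**4. What does not follow.** Compare instead with a 7-day rate counted from admission. Illustrative assumptions, not in the plan: that rate is 5.3%, all patients stay to day d+7, and the cumulative hazard is H × (t/7)^k with H = −ln(1 − 0.053) = 0.0545. The measured rate is 1 − exp(−H × [((d+7)/7)^k − (d/7)^k]).

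Worked case, d = 3:

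- k = 0.5 (risk highest early): 0.0545 × (1.195 − 0.655) = 0.0294, giving 2.9%.
- k = 1 (constant): 0.0545 × 1 = 0.0545, giving 5.3%.
- k = 1.5 (risk rising): 0.0545 × (1.707 − 0.281) = 0.0777, giving 7.5%.

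| Entry day d | k = 0.5: measured (admission to d+7) | k = 1 | k = 1.5 |
|---|---|---|---|
| 1 | 3.7% (5.7%) | 5.3% (6.0%) | 6.2% (6.4%) |
| 3 | 2.9% (6.3%) | 5.3% (7.5%) | 7.5% (8.9%) |
| 7 | 2.2% (7.4%) | 5.3% (10.3%) | 9.5% (14.3%) |

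In every cell the measured rate is below the bracketed one, as step 3 requires. Against 5.3% it can be lower, equal or higher.

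**The case against.** The strongest reply is that the plan already says what it measures. The objective in section 3.1 is confined to injuries arising while the dressing is worn, the endpoint is confined to the investigation period, and a prevention question needs patients who are uninjured at the start. This stands: the exclusion is legitimate and should remain. It does not rescue the label in 10.1, the justification in 6.2, or a comparison whose basis is unstated.

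Second, the external trial may also have enrolled patients with intact skin and counted from enrolment. If so, this feature alone creates no bias against the 5.3%. This also stands, and it is why no direction is claimed against that figure.

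Third, admission date is not simply ignored. Section 10.1 lists and summarises baseline assessments and allows further exploratory analyses on subsets. That is fair. What is missing is the interval from admission to V1 as a defined variable, and any stated use of it.

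Fourth, patients still in hospital at a late screening may be at higher risk than the average admission, which would push the rate up. The documents cannot exclude this, and it too argues against asserting a direction.

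**Conclusion.** The point holds as a mismatch between estimate, label and comparison. The estimate is the proportion developing a sacral pressure injury after dressing application, over up to 7 days or until discharge, among patients free of sacral injury and erythema at V0/V1. It is not a hospital-acquired incidence counted from admission, and the justification in 6.2 contradicts the timing of the check.

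On size, the estimate is below a rate counted from admission to the same day in the same admitted population. The amount cannot be computed, because the plan gives no admission-to-V1 times. The 2.2% to 9.5% range is an illustration that rests on the assumed 5.3% seven-day risk, the assumed hazard shapes and a complete 7-day follow-up.

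A reader might go further and infer that the result is biased low, in favour of the dressing, against the 5.3% [2.3%; 10.1%] and the literature rates. The documents do not support that: they do not say when those rates began counting or how existing injuries were handled, and the direction can change with the hazard. A reader might also estimate the share of injuries missed as days of delay divided by length of stay. That works only if total stay is fixed, and it ignores the follow-up of up to 7 days from V1, so it does not describe this design.

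**What to change.** - **Section 10.1:** name the estimate *incidence of sacral pressure injury from dressing application, in patients injury-free at V1*.
- **Section 6.2:** change the justification so that it refers to screening/V1 and not to admission.
- **Section 10.1, reporting:** derive time from admission to V1 from the admission date already collected, and summarise it. Show the injury proportion by that time, for example in an early-entry subset, only as a descriptive sensitivity display beside the full sample. Label it post hoc if the data have been seen.
- **Sections 10.2 and 10.4:** for each external rate, state when observation began and how existing injuries were handled. Limit comparative conclusions to rates counted on the same basis.

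Two further steps are not recommended. Making an early-entry subset the main comparison would help only if the external rates started at admission, which is unknown. Counting exclusions for injuries that arose after admission would need skin status at admission, which the plan does not collect.

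The cost is wording, one derived variable and a check of the cited sources; no new patient assessments are needed. The subset would be small. If 25 of the 50 completers qualified (an assumption), zero events would still give an exact two-sided upper limit of 1 − 0.025^(1/25) = 13.7%, above the comparator's 10.1%. The permitted conclusion also becomes narrower.
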